5.4.1 Timing of Interim Prenatal Follow-Up

At the end of the second trimester, the Registry again contacts the obstetric HCP to obtain interim follow-up information on maternal medications including dose, duration, and dates of use, medical conditions, and pregnancy status.

5.4.2 Information Collected at Interim Prenatal Follow-up

Savella, Other Medication Exposure Information, and Concurrent Medical Conditions

- Medication (Savella, or other medications, including herbals and dietary supplements)
 - Total daily dose with units
 - Route of administration
 - Gestation week the treatment course began and how the gestation week was calculated (from LMP or CEDD)
 - Start date of treatment course
 - Gestation week or stop date of the treatment
- Concurrent medical conditions (including complications of pregnancy such as gestational hypertension, pre-eclampsia, eclampsia, gestational diabetes, etc)
- Tobacco use during pregnancy
- Alcohol use during pregnancy
- Recreational drug use during pregnancy

Pregnancy Status

- CEDD
- If a subsequent prenatal test (diagnostic or screening) has indicated a birth defect or other abnormality
- Pregnancy outcome (live birth (full-term or pre-term), spontaneous abortion, stillbirth, ectopic pregnancy, induced abortion (elective or therapeutic), molar pregnancy) and as applicable:
 - Date of outcome of pregnancy
 - Gestational age at outcome
 - Gender
 - Birth weight
 - Birth defect noted
 - Type of birth defect(s) if applicable, attribution to Savella therapy, and other factors that might have contributed to the outcome
 - Chromosomal abnormalities and details, if noted

- Evidence of alterations in fetal growth
- For a fetal loss (spontaneous abortion, stillbirth): Birth defects or other factors that may have had an impact on the fetal loss and attribution to Savella therapy

5.5 Follow-up Evaluation at Pregnancy Outcome

5.5.1 Timing of Pregnancy Outcome Follow-Up

In the month of the expected date of delivery, the Registry prompts the pregnant patient's obstetric HCP to complete the **Obstetric Follow-Up Form**. The patient is also contacted to obtain contact information for the baby's pediatrician and a medical release.

Obstetric Follow-up Form

5.5.2 Information Collected at Pregnancy Outcome Follow-up

Fetal outcome (for each outcome if multiple gestation)

- Pregnancy outcome: live birth (full-term or pre-term), spontaneous abortion, stillbirth, ectopic pregnancy, induced abortion (elective or therapeutic), molar pregnancy
- Date of outcome of pregnancy
- Gestational age at outcome
- Gender
- Birth weight
- Birth defect noted
- Type of birth defect(s) if applicable, attribution to Savella therapy, and other factors that might have contributed to the outcome
- For a fetal loss (spontaneous abortion, stillbirth): Birth defects or factors other than birth defects that may have had an impact on the fetal loss and attribution to Savella therapy

Maternal Complications

• Gestational hypertension, pre-eclampsia, eclampsia

5.6 Follow-up Evaluation by Pediatrician for Live Births

5.6.1 Timing of Pediatric Follow-Up

If a live birth occurs, the mother is asked to give consent for the infant's pediatrician to provide follow-up information. If consent is obtained, the pediatrician completes the **Pediatric Follow-Up Form** immediately after birth, at 4 months, and 12 months of age.

Pediatric Follow-up Form

5.6.2 Information Collected at Pediatric Follow-up

Infant at outcome

- Date of follow-up evaluation
- Current age of infant (at the time of assessment)
- Gender
- Gestational age at birth
- APGAR scores at birth
- Birth weight, length, head circumference and corresponding population-based percentiles
- Birth defect(s) and details, if noted
 - Type of birth defect(s)
 - Attribution to Savella drug therapy
 - Other factors that might have contributed to the outcome
 - Defect absent/present on pre- or post-natal test
- Chromosomal abnormalities and details, if noted
- Immediate post-natal health problems requiring resuscitation, admission to the neonatal intensive care unit (NICU)
- Medications
- Surgical interventions required of pre-term infants
- Other serious infant adverse outcomes noted on physical examination
 - Evidence of alterations in fetal/infant growth (e.g., intrauterine growth restricted, small for gestational age, etc.)
 - Presence of functional deficit (e.g., poor muscle tone, abnormal reflexes)
 - Presence of biochemical abnormality
 - Presence of transient or infectious conditions
 - Symptoms of poor neonatal adaptation (i.e., neonatal withdrawal)
 - Persistent pulmonary hypertension of the newborn

Infant at 4 and 12 months

- Date of follow-up evaluation
- Current age of infant (at the time of assessment)
- Birth weight, length, head circumference and corresponding population-based percentiles
- Birth defect(s) detected since last assessment and details, if noted
 - Type of birth defect(s)
 - Attribution to Savella drug therapy
 - Other factors that might have contributed to the outcome
 - Defect absent/present on pre- or post-natal test
- Chromosomal abnormalities and details, if noted
- Medications
 - Other serious infant adverse outcomes noted on physical examination

- Evidence of alterations in infant growth
- Presence of functional deficits
- Developmental delays

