2. PURPOSE AND RATIONALE

The purpose of Allergan's Savella Pregnancy Registry (Registry) is to monitor pregnancies exposed to Savella (milnacipran HCl) to determine the risk of birth defects. Because Savella is commonly used among reproductive age women, this pregnancy registry has been established to prospectively assess the birth outcomes of babies born to women that are exposed to Savella during pregnancy. The lack of human fetal safety data concerning this product makes such a monitoring system an important component of epidemiologic research on the safety of Savella. Due to the lack of human data regarding fetal safety, the Registry is primarily exploratory.

The primary objective of the Savella Pregnancy Registry is:

• To estimate the prevalence of major congenital anomalies among offspring of women exposed to Savella during pregnancy.

The secondary objectives are

- To estimate the prevalence of full-term live births (≥37 weeks), pre-term live births (<37 weeks), recognized spontaneous abortions, stillbirths, induced abortions (elective and therapeutic), chromosomal abnormalities, and minor congenital anomalies
- 2) To summarize
- Serious pregnancy complications and maternal adverse events
- Adverse pregnancy outcomes
- Serious adverse outcomes observed during the first year of life in infants born from exposed pregnancies, including alterations in fetal/infant growth, presence of functional deficits, biochemical abnormalities, transient or infectious conditions, symptoms of poor neonatal adaptation (i.e., neonatal withdrawal), and persistent pulmonary hypertension of the newborn

3. **REGISTRY DESIGN**

This is a prospective, observational, exposure-registration and follow-up registry of women exposed to Savella during pregnancy. The Registry is strictly observational; the schedule of patient visits and treatment regimens are at the discretion of the treating physician. HCPs submit patient data that are routinely collected and documented in the patient's medical record.

4. **REGISTRY POPULATION**

The Registry population includes women with any Savella exposure during pregnancy, defined as exposure on or after the first day of the LMP. Women must be \geq 18 years of age and reside in the US.

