5. GENERAL REGISTRY PROCEDURES

Enrollment may be initiated by pregnant patients or their HCPs. Patients are followed through their HCPs who are willing to provide information on maternal risk factors, pregnancy outcome, and infant health. Patient reports must be verified with an HCP. Section 5.3 describes this process in detail.

Enrollment should occur as early in pregnancy as possible, preferably before any prenatal testing has occurred; however, enrollment at any time during pregnancy is allowed. Near the estimated date of delivery, the Registry prompts the HCP to provide pregnancy outcome data. If a birth defect is reported, the Registry requests additional targeted follow-up information from the HCP. Follow-up of live-born infants continues through the first year of life.

Summary of Evaluations

	Maternal Contact		Maternal HCP Contact			Infant HCP Contact		Evaluator
Information Requested	Enrollment	Outcome	Registration	Interim Follow-Up (2 nd trimester)	Outcome Follow-Up	Follow-Up (at birth)	Follow-Up (4 and 12 months)	Targeted Follow-Up
Reporter Information and Permissions	_	-				-	-	-
Report source, permission to contact HCP (for pregnant patient), pediatrician, and alternate patient contact information as applicable (see section 5.3.1)	1	√ ^a	4					
Maternal Information								
Maternal characteristics (age, ethnicity, disease status)	1		✓					
Maternal prenatal information (LMP, EDD, CEDD, prenatal test results & timing)	1		1	√ ^a	√ ^a			
Obstetrical history, family history (maternal and paternal)	✓		1					✓ ^d
Savella therapy (dosage, routes, start/stop dates)	1		1	√ ^a	√ ^a			
Concomitant medications (Rx, OTC, dietary supplements, herbals), during pregnancy (dosage, routes, start/stop date of administration), and alcohol, tobacco, and recreational drug use during pregnancy	4		~	√ ^a	√ ^a			√ ^d
Maternal concurrent medical conditions, pregnancy complications, maternal adverse events	1		1	√ ^a	√ ^a			
Outcome of Pregnancy Information								
Pregnancy Status	✓	✓	✓	✓	√ ^a			
Outcome data (fetal loss, live birth, gestational age, weight)		✓		✓ ^b	✓	✓		
Birth defect noted, description, attribution, if applicable				✓ ^b	✓			
Other factors that may have contributed to outcome (etiology)				✓ ^b	✓			✓ ^d
Infant Follow-up Information								
Infant assessments: anthropometric, developmental, functional, growth, postnatal conditions, medications,						✓ ^b	1	
Birth defect noted, description, attribution, if applicable						√ ^b	1	

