8.5.4 Infant Follow-Up

Descriptive statistics will be presented for infant outcomes including mean gestational age at outcome, mean birth weight, medications, head circumference, APGAR scores, immediate post-natal health problems requiring resuscitation or admission to the NICU, and developmental milestones

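### The 4- and 12-month infant data list in section 5.6.2 repeats birth weight and names no weight at the time of assessment, which weakens the first-year growth objective.

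*Protocol*

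**What the plan says.** Among its secondary aims, Protocol section 2 sets out to summarise "Serious adverse outcomes observed during the first year of life in infants born from exposed pregnancies, including alterations in fetal/infant growth". Section 5.6.1 has the paediatrician complete the Pediatric Follow-Up Form "immediately after birth, at 4 months, and 12 months of age". The Summary of Evaluations in section 5 marks the row "Infant assessments: anthropometric, developmental, functional, growth, postnatal conditions, medications" for the infant healthcare provider contact at 4 and 12 months.

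Section 5.6.2 then gives the content in two lists, one for the infant at outcome and one for the infant at 4 and 12 months. The body-size item in both is "Birth weight, length, head circumference and corresponding population-based percentiles". The later list also has "Current age of infant (at the time of assessment" and, as a reported finding, "Evidence of alterations in infant growth".

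On analysis, section 8.5.4 promises descriptive statistics that include "mean birth weight, medications, head circumference, APGAR scores". Section 8.5.3 lists altered fetal growth among the outcomes to be counted.

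**The concern.** Birth weight does not change after delivery. By the 4-month contact it has already been requested on the obstetric outcome form (section 5.5.2) and on the paediatric form at outcome (section 5.6.2). Asking for it at 4 and 12 months adds nothing, and weight at those ages is not requested anywhere.

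Follow-up to 12 months is partly meant to show whether growth is altered after exposure. Without attained weight the Registry cannot describe weight for age at either contact, show movement across weight percentiles, or set a reported growth alteration against a weight. An analysis plan cannot repair this later, because it can only use data that were collected.

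**Working it through.** No formula or planned figure is at issue, so the check is a comparison of the passages.

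**1. The two lists in section 5.6.2.**

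| Item | Infant at outcome | Infant at 4 and 12 months |
|---|---|---|
| Gender, gestational age, APGAR | listed | dropped |
| Birth defects | those noted | those found since the last assessment |
| Growth finding | fetal or infant growth, with examples | infant growth only, no example or criterion |
| Developmental delay | not listed | added |
| Body size | birth weight, length, head circumference, percentiles | identical wording |

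Most of the later list was adapted for an older infant. The body-size line was not. That pattern points to text carried over by mistake, not to a decision to leave weight out.

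**2. The schedule.** The Summary of Evaluations calls for anthropometric and growth assessment at 4 and 12 months. The later list also asks for the infant's age at the assessment. Both imply that current body size is wanted.

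**3. Two readings of the line.**
- If the word birth qualifies only weight, length and head circumference with percentiles are current values and only attained weight is missing. This is the natural reading.
- If it qualifies all three measures, no current body measurement is specified after birth.

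On either reading, attained weight is absent.

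**4. What can be derived.** Weight gain to 4 or 12 months is weight at that age minus birth weight. The list supplies only the second term, up to four times per infant: obstetric outcome form, then paediatric form at outcome, 4 months and 12 months. Weight gain and the attained-weight percentile therefore cannot be formed from the listed data.

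**5. Other sections.** Section 8.5.4 names birth weight and head circumference but not attained weight. The growth outcome in section 8.5.3 is fetal. Neither supplies the missing item.

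**6. How many infants.** Section 8.4 expects 196 live births from 350 pregnancies (350 × 0.90 × 0.62 = 195.3). That is not the number assessed at 4 or 12 months. Paediatric follow-up needs the mother's consent (section 5.6.1), and infants can be lost to follow-up (section 6.2.7). The protocol gives no rate for either, so the number assessed cannot be stated.

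**The case against.** The strongest reply is that this is a wording slip with little consequence. Several parts of that reply stand.

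- A reader might infer that the growth objective is left to unstandardised clinician opinion. The documents do not support this. On the natural reading, length and head circumference with population percentiles are current, standardised measures at both ages.
- A reader might infer that weight is certainly uncollected for all 196 infants. The Pediatric Follow-Up Form is not reproduced, only the protocol's list of its content, so the form may ask for current weight. As shown above, 196 is also not the number of infants assessed.
- The objective is to summarise serious adverse outcomes. It does not promise growth curves or change from birth, and a provider's report of altered growth is a legitimate measure in a registry built on routine records.
- Detailed tables by visit and change scores can be left to the statistical analysis plan, so their absence from section 8.5.4 is no fault.

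None of this puts weight into the 4- and 12-month list. That list says what is collected, and it conflicts with the protocol's own schedule. If the form is already right, the protocol text still needs to agree with it.

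**Conclusion.** The point holds in a limited form. As written, section 5.6.2 specifies no weight after birth, so attained weight, its percentile and weight gain are not among the data for any infant followed under that list. This weakens a descriptive secondary objective but does not empty it. Length, head circumference, their percentiles and the reported growth finding remain, as do the other items at 4 and 12 months. The primary estimate of birth-defect prevalence is unaffected.

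The conclusion assumes that the form follows the protocol's list and that the word birth qualifies weight only. If it qualifies all three measures, the gap widens to all body measurements after birth. The documents do not show that anyone chose to omit weight. The correction is worth making because the list determines what data the Registry will hold.

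**What to change.** In the 4- and 12-month list of section 5.6.2, replace the body-size line with: weight, length and head circumference measured at this assessment, each with its population percentile. This also settles which reading applies to length and head circumference. Check the Pediatric Follow-Up Form and bring it into line. If it already asks for current weight, only the protocol text changes. In section 8.5.4, add weight at 4 and 12 months to the descriptive summary beside birth weight, and leave the table layout to the statistical analysis plan.

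The cost is one extra field at each of two contacts. That is at most 2 × 196 = 392 values if every expected live birth were followed to 12 months. No visit or procedure is added, since section 3 limits the data to what is routinely recorded. The protocol does not say that weight is recorded at these visits, so some values may be missing and should be reported as such.

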5.7 Targeted Follow-Up

5.7.1 When is Targeted Follow-Up Conducted?

If a birth defect is noted at pregnancy outcome, or at any time during the infant follow-up period, additional details regarding the birth defect are requested from the maternal and/or pediatric provider, as appropriate, using the **Targeted Follow-up Form**, to facilitate classification and to assess the presence of potential confounders.

Targeted Follow-up Form

5.7.2 Information Collected at Targeted Follow-up

- Details of the birth defect, chromosomal abnormality, or other condition warranting teratology follow-up.
 - The Targeted Follow up form is individualized to the unique history and presentation of each potential defect case.
 - The specific term used to describe the condition under review (i.e, birth defect, chromosomal abnormality, or other condition) is entered on the Targeted Follow up form,
 - Specific questions requested by the sponsor and/or the birth defect evaluator reviewing the case are also entered on to this form.
 - Etiology
 - Outcome attribution

6. METHODS AND PROCESSES

6.1 Registry Awareness / Recruitment

The Registry can be accessed by text, phone or internet (www.savellapregnancyregistry.com)

The Registry phone number of [contact] is available in the following locations:

- 1) Savella prescribing information
- 3) Allergan website (www.Allergan.com) and/or Savella website (www.Savella.com)
- 4) FDA website listing pregnancy registries: http://www.fda.gov/womens/registries/default.htm
- 5) INC Research InVentiv Health website: https://www.incresearch.com/what-wedo/standalone-services/cro-pregnancy-registries
- 6) ClinicalTrials.gov
- 7) Others as deemed appropriate

At initiation, the Registry may conduct a direct mailing of Registry information to healthcare professionals who might provide patients to the Registry. These healthcare professionals are identified through professional organizations (e.g., appropriate professional societies for fibromyalgia), and large academic medical centers specializing in the relevant fibromyalgia and high-risk obstetrics. Additional venues for increasing awareness of the Registry include: 1) providing Registry methods presentations at scientific or clinical meetings (e.g., ACOG) and 2) dissemination of Dear Doctor Letters to a variety of specialties. For example, 136,242 Dear Doctor Letters were sent to HCPs in 15 specialty areas in 2011; of which, 84,379 were family practice HCPs and 1,479 were obstetrics/gynecology HCPs. Therefore, included in these awareness efforts is contact with HCPs caring for women during their pregnancies, particularly, early in pregnancy. In addition, the Registry enlists the aid of the FDA, Centers for Disease Control and Prevention (CDC), the Organization of Teratogen Information Services (OTIS), and other relevant organizations in facilitating patient recruitment.

6.2 Registry Case Report Management

Reports that come to the Registry are first classified as either prospective or retrospective. They are further classified as complete, valid, not verified by the HCP, lost to follow-up, invalid, or duplicate. All reports that come to the Registry are summarized for Allergan safety reporting purposes in the annual line-listings. Evaluable reports are evaluated and accounted for in the Registry Interim/Final Report. However, only the prospective reports are included in the primary analysis and statistical calculation of risk.

6.2.1 Prospective Registry Reports

Prospective reports are reports provided during pregnancy, following an exposure to Savella, but before prenatal tests have been conducted that provide information on the outcome of the pregnancy. In order to achieve adequate numbers, only those pregnancies with anomalies or other abnormalities identified on a prenatal test are considered as retrospective reports. Those with no abnormalities noted on prenatal tests are considered prospective and included in the primary analysis. Section 8.6 addresses the potential bias introduced by this practice in more detail.

6.2.2 Retrospective Registry Reports

A report is considered retrospective when an abnormality has been identified on a diagnostic or screening prenatal test at the time of initial reporting. Additionally, retrospective reports for which the pregnancy outcome has already occurred will only be accepted if the following two criteria are met, 1) a birth defect was noted, and 2) the outcome occurred within two years of the time of the initial report.

Retrospective reports can be biased toward the reporting of more unusual and severe outcomes and are less likely to be representative of the general population experience. Therefore, the inclusion of such reports in the calculation of risk is inappropriate. Retrospective reports with birth defects and/or spontaneous fetal losses are reviewed to aid in detecting early signals, but they are not included in the statistical analysis.

Occasionally, the Registry may receive retrospective reports of exposed pregnancies resulting in normal outcomes. Although the Registry does not actively solicit this type of

information, the data will be recorded on a contact form and then entered into a log which is separate from the analysis database.

6.2.3 Evaluable Registry Reports

An evaluable report is a case, submitted or verified by a HCP, containing at least the minimum criteria for Registry enrollment, and is not lost to follow-up. Prospectively reported evaluable cases with known outcomes are included in the primary analyses for the Interim Report produced annually and the Final Report. Retrospective reports are summarized separately in the Interim Reports and the Final Report.

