8. STATISTICAL CONSIDERATIONS

8.1 Analysis Population

The primary population for analysis includes prospective evaluable cases that are not "lost to follow-up" (i.e., cases with appropriate outcome information and meeting the minimum criteria for evaluation). Retrospective cases are reviewed and reported separately.

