8.5.3 Adverse Pregnancy Outcomes

Overall and by-stratum point estimates of rates and 95% confidence intervals will be calculated for the following outcomes:

- Spontaneous abortions
- Stillbirths
- Induced abortions (overall and elective or therapeutic)
- Minor congenital anomalies,

Other adverse pregnancy outcomes among pregnancies exposed to Savella and their live births during the first year of life will be summarized as counts and percentages of the total number of prospective evaluable outcomes. Summaries will also be presented by subgroups including maternal age at conception (<25, 25-35, >35), family history of birth defects, smoking status, and alcohol use during pregnancy. Additional subgroups may be analyzed if deemed appropriate and necessary given the sample size. These other adverse pregnancy outcomes include:

- Functional deficits
- Alterations in fetal growth
- Transient or infectious conditions
- Biochemical abnormalities
- Pre-term infants with findings that persist and require surgical intervention

Strata are comprised by earliest trimester of exposure and potentially other variables as appropriate given the sample size, such as maternal age, history of birth defects, lifestyle variables, comorbidities, and concomitant drug exposures.

All chromosomal abnormalities, whether classified as a birth defect or other adverse outcome, will be displayed in a separate listing.

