8.6 Potential Biases

Because early prenatal testing is so prevalent in the US, it may be difficult to achieve adequate numbers of prospectively identified patients if all pregnancies with prior prenatal testing are excluded from the analysis. Therefore, the primary analyses includes pregnancies enrolled prior to outcome but after a prenatal test as long as the test does not indicate an abnormality. However, this practice could potentially bias the results by lowering the overall risk of birth defects (Honein et al., 1999). The analysis attempts to address whether this practice biases the results.

As reporting of pregnancies is totally voluntary, it is possible that even in prospectively reported cases, potential bias could exist. For example, high-risk pregnancies or low-risk pregnancies may be more likely to be reported.

Enrolled pregnancies that have reached their estimated date of delivery and for which outcome information is unobtainable are considered "lost to follow-up". It is possible that outcomes among pregnancies lost to follow-up could differ from those with documented outcomes. Because of differences in follow-up and reporting patterns, it is currently not possible to assess with any certainty what impact the potential biases the losses to follow-up may have on the analysis. However, efforts at comparing some of the characteristics of each group are conducted in an attempt to address this potential source of bias.

Following the MACDP convention, calculation of birth defect risk excludes fetal losses (spontaneous abortions, induced abortions, stillbirths, etc.) for which no birth defects have been detected as they may introduce a classification bias. It is unknown what percentage of these pregnancies consists of potentially normal outcomes or birth defects. The Registry attempts to obtain information on birth defects detected at the time of the outcome. However, the reporting physician may not know the condition of the aborted fetus.

While the Registry analysis is limited to prospective reports, some pregnancy exposures are reported following pregnancy outcome (retrospective cases). Each retrospective report is carefully reviewed. In general, retrospective reports of exposures to therapy following notification of outcome are biased toward reporting the severe and unusual

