9.1 Regulatory Agency Reporting Considerations

The Registry follows the FDA Guidance for Industry, *Establishing Pregnancy Exposure Registries* (FDA, 2002) for regulatory reporting of adverse events to FDA. "The Agency considers pregnancy exposure registry reports (both prospective and retrospective) as derived from active solicitation of patient information." Therefore Allergan is responsible for, "reporting any serious and unexpected events by regulatory definition and where a reasonable possibility exists that the drug or biological product caused the adverse event within 15 calendar-days" (FDA, 2002).

For FDA status reporting, the Registry Interim Report can be appended to the annual report submission as described in the FDA Guidance (FDA, 2002). The Interim Report, published annually, contains the background, Registry design, and analysis plan. It summarizes the status and the cumulative data on the Registry to date. In addition, the Registry can generate individual case line listings to assist Allergan in preparation of its submission. The Interim Report, generated annually, is cumulative and current to the most recent data cutoff period.

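### Annual interim rates count a pregnancy once its outcome is known, with no requirement that its due date has passed, so early losses are over-represented in the secondary loss rates, mainly in the first reports

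*Protocol*

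**What the plan says.** The inclusion rule is in Section 6.2.3: "Prospectively reported evaluable cases with known outcomes are included in the primary analyses for the Interim Report produced annually", and the same sentence extends it to the Final Report. Section 8.1 repeats it for the primary analysis population, which consists of "cases with appropriate outcome information and meeting the minimum criteria for evaluation". Section 9.1 fixes the timing: "The Interim Report, generated annually, is cumulative and current to the most recent data cutoff period".

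Section 8.5.3 covers spontaneous abortions, stillbirths, induced abortions and minor anomalies: "Overall and by-stratum point estimates of rates and 95% confidence intervals will be calculated for the following outcomes". It does not spell out their denominator. For the other adverse outcomes the same section does give one; these "will be summarized as counts and percentages of the total number of prospective evaluable outcomes".

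Section 8.6 brings in the EDD only to define loss to follow-up: "Enrolled pregnancies that have reached their estimated date of delivery and for which outcome information is unobtainable are considered" lost to follow-up. A pregnancy that is still continuing at the cut-off is therefore not lost, has no outcome, and is absent from the rate.

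**The concern.** Whether a pregnancy is in the analysis at a given cut-off depends on how it ends. Take two women who enrol at 10 weeks shortly before the cut-off. If one miscarries at 13 weeks, she can be counted 3 weeks after enrolment. If the other delivers at 39 weeks, she is not counted until 29 weeks after enrolment. While enrolment is open, each cumulative report therefore holds more of the short pregnancies than of the long ones.

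The prevalence of live births, spontaneous abortions, stillbirths and induced abortions is a stated secondary objective (Section 2). Interim reports go to the FDA each year, and the advisory committee reviews the accumulated data each year. An artificially high early loss rate that falls from report to report could be misread as a real trend. Section 8.6 discusses prenatal testing, voluntary reporting, loss to follow-up, fetal losses without a detected defect and retrospective reports. It does not mention this mechanism.

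**Working it through.** **The plan's own figures.** The protocol gives no interim loss rate to reproduce. Its sample-size figures do reproduce: 350 × 0.62 × 0.90 = 195.3, rounded up to 196 live births. The exact binomial power for 6.95% against 2.78% is 80.7% (reject at 11 or more cases, upper-tail alpha 0.0221).

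**Inputs from the protocol.**
- Live-birth share 62%, hence 38% other outcomes (Section 8.4).
- A routine provider contact at the end of the second trimester ("At the end of the second trimester, the Registry again contacts the obstetric HCP to obtain interim follow-up information", Section 5.4.1), which is 28 weeks by the definition in Section 8.2.
- The outcome contact in the month of expected delivery (Section 5.5.1).

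**Assumptions.**
- Uniform accrual and a 52-week year.
- Enrolment at 10 weeks.
- Live birth at 39 weeks, known at once, so the lag is 29 weeks.
- A spontaneous abortion known either when it occurs at 13 weeks (lag 3 weeks) or only at the 28-week contact (lag 18 weeks).
- A true spontaneous abortion risk of 15%.

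**Formula.** After T weeks of accrual, the fraction of each outcome type already known is (T − lag)/T. The reported rate is

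p(T − lag_loss) / [p(T − lag_loss) + (1 − p)(T − lag_birth)].

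**Year 1, p = 15%.**
- Loss known at 13 weeks: 0.15 × 49 = 7.35 and 0.85 × 23 = 19.55, so 7.35/26.90 = 27.3%.
- Loss known at 28 weeks: 0.15 × 34 = 5.10, so 5.10/24.65 = 20.7%.

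| Years of accrual | Loss known at 13 weeks | Loss known at 28-week contact |
|---|---|---|
| 1 | 27.3% | 20.7% |
| 2 | 19.2% | 16.8% |
| 3 | 17.5% | 16.1% |
| 5 | 16.4% | 15.6% |
| 6 | 16.2% | 15.5% |
| 8 | 15.8% | 15.4% |

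**The protocol's own 38%.** With a loss lag of 4 weeks, year 1 gives 0.38 × 48 = 18.24 against 0.62 × 23 = 14.26, so 18.24/32.50 = 56.1%. With a lag of 18 weeks it gives 12.92/27.18 = 47.5%. At year 2 the figures are 45.0% and 41.3%. This is an illustration only, because it gives all non-live outcomes a single lag, and stillbirths by definition occur at 20 weeks or later.

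**Sensitivity.** True shares of 10%, 20% and 38%, enrolment at 10 or 20 weeks, losses known 4 weeks after enrolment or at 28 weeks, and births known at 40 weeks give these relative inflations: about 20-94% at year 1, 8-30% at year 2, 3-10% at year 5 and 2-6% at year 8.

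**With an EDD restriction.** Both outcome types then wait for the same date, the two lags are equal, the (T − lag) terms cancel, and the formula returns p exactly.

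**Defect analyses (Section 8.5.1).** The primary prevalence divides by live births. Early losses are not in that denominator, and only defects in losses at or after 20 weeks can reach the numerator ahead of comparable live births. The secondary analysis that adds defects in losses at any gestational age is more exposed, because those defects enter early while the live births enter late.

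**The case against.** The strongest reply is that the effect is small where this version applies. Version 3.1 is dated September 2017, the product was approved in January 2009, and awareness letters went out in 2011. No start date for accrual is given, but if it was around 2011, reports under this version begin at about year 6, where the excess is about 1 point at most. For comparison, with about 350 × 0.90 = 315 outcomes the 95% interval half-width at 15% is 1.96 × √(0.15 × 0.85/315), about 4 points. That stands, and it is why the point is minor.

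The year-1 figure of 27% also assumes that losses are reported at once. The scheduled contacts support a later date, hence the range of 21-27%.

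The denominator for the loss rates is inferred from Sections 6.2.3, 8.1 and 8.5.3 taken together, and the SAP, not seen here, may add detail. That stands as a caveat. However, Section 6.2.3 sets a positive inclusion rule, so an EDD rule that appeared only in the SAP would conflict with it.

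A reader might infer more than the protocol supports:
- **That the primary result is distorted.** Its denominator is live births, so it is little affected.
- **That a false signal or an early stop would follow.** The Rule of Three and the case review in Section 7.3 concern birth defects, Section 8.2 says that confidence intervals are not used for inference, and no discontinuation criterion in Section 14 depends on a loss rate.
- **That the final report shares the bias.** It does so only if its cut-off precedes some EDDs. With infants followed to 12 months before closure, every EDD would have passed.
- **That the reported rates exceed the population risk.** Enrolment at any gestational age misses early losses and pulls the rates down, so the net error is unknown.

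**Conclusion.** The concern holds as a minor point about secondary, descriptive interim rates. While enrolment is open, the known-outcome rule raises the rates of spontaneous and induced abortion, and to a lesser degree stillbirth, relative to the same cohort followed to completion, and it understates the live-birth share. The secondary defect analysis at any gestational age is exposed in the same way.

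The direction follows from the rule together with the inferred denominator. The size rests on assumed uniform accrual, enrolment age and reporting lag. It is substantial only in the first one or two reports and is about 1 point or less by years 6 to 8. The protocol neither corrects the effect nor lists it among its biases.

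**What to change.** In Sections 6.2.3 and 8.1, state that interim and final pregnancy-outcome rates are computed among prospective evaluable pregnancies whose EDD (corrected EDD where available) is on or before the data cut-off, whatever the actual date of outcome. List pregnancies with a later EDD as pending, and show any losses or defects among them case by case so that signal review loses nothing. Set the final cut-off after the EDD of the last enrolled pregnancy.

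The cost is a short addition to the protocol, with matching text in the SAP. Some recent outcomes enter the rates one report later but stay visible in the listing. A small residual remains for pregnancies just past their EDD whose forms are not yet back; a count of these in each report would show how many there are.
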